11.2.2. Primary analyses

For primary VE objectives 1-2, the number of incident HZ cases and the number of person-years of follow-up for subjects will be assessed for the 2-dose (4 weeks to 6 months) RZV cohort and the matched unvaccinated cohort.

Unadjusted and adjusted HRs and 95% confidence intervals (CIs) comparing HZ incidence rates in the 2-dose (4 weeks to 6 months) RZV cohort and the matched

unvaccinated cohort will be estimated by Cox stratified proportional hazards regression models without and with adjusting for potential confounders described above. Estimates of VE (%) will be calculated as $(1 - \text{HR}) \times 100$ when the HR is less than or equal to 1, and $([1/\text{HR}] - 1) \times 100$ when the hazard ratio is greater than 1.

The VE of 2 doses of RZV by time since vaccination will also be evaluated.

For the primary safety analyses, characteristics of individuals with RA or IBD who meet inclusion criteria will be described. Incidence rates for RA or IBD (UC or CD) flare for risk periods and comparison periods will be calculated by dividing the number of flares by person-time. Relative risks (95% CI) for flare comparing risk and comparison periods overall and by first dose and second dose will be estimated using conditional Poisson regression.

11.2.3. Secondary analyses

For secondary and exploratory analyses, subgroups may be recategorized in post-hoc analyses if sample size in a subgroup is small

Secondary VE objectives 1-3: Analyses for secondary VE objectives 1-3 (2 doses of RZV given at least 4 weeks apart) will employ similar methods as for the primary VE analyses. In secondary VE objective 1, analyses for IBD (primary VE objective 2) will be stratified by UC and CD. In secondary VE objective 2, analyses for RA (primary VE objective 1) will be stratified by age group (18-49 years and ≥ 50 years [≥ 50 years, 50-59 years, 60-69 years, and ≥ 70 years]). In secondary VE objective 3, analyses for IBD (primary VE objective 2) will be stratified by age group (18-49 years and ≥ 50 years [≥ 50 years, 50-59 years, 60-69 years, and ≥ 70 years]). Descriptive analyses and multivariable Cox proportional hazards regression will be conducted by strata and estimates of VE (%) will be calculated as $(1 - \text{adjusted HR}) \times 100$.

Secondary VE objectives 4-5: Analyses for secondary VE objectives 4-5 will employ similar methods as for the primary VE analyses. For secondary VE objective 4, the 2-dose RZV cohort will include individuals who receive their second dose >6 months after the first dose during the accrual period. For secondary VE objective 5, the 2-dose RZV cohort will include individuals who receive their second dose at least 4 weeks after the first dose during the accrual period. Analyses will be stratified by condition (RA or IBD). The VE of 2 doses (≥ 4 weeks apart) of RZV by time since vaccination will also be evaluated.

Secondary VE objectives 6-7: Analyses for secondary VE objectives 6-7 will be conducted among the matched cohorts of individuals with RA (secondary VE objective 6) or with IBD (secondary VE objective 7) who receive 1 dose of RZV and do not receive a second dose within 6 months after the first dose. Individuals will be followed from 31 days after the index date until occurrence of HZ, termination of membership, receipt of a dose of RZV for unvaccinated individuals, receipt of a second dose of RZV >6 months after the first dose among vaccinated individuals, or end of study period, whichever comes first. Descriptive analyses and multivariable Cox proportional hazards

regression will be conducted and estimates of VE (%) will be calculated as $(1 - \text{adjusted HR}) \times 100$. The VE of 1 dose of RZV by time since vaccination will also be evaluated.

Secondary safety objective 1: Analyses for IBD will be stratified by UC or CD.

11.2.4. Exploratory analyses

Exploratory VE objectives 1-2: Analyses for exploratory VE objectives 1-2 (2 doses of RZV given at least 4 weeks apart) will employ similar methods as for the primary VE objectives. In exploratory VE objective 1, analyses for RA (primary VE objective 1) will be stratified by medication category at index date ([Appendix 3](#)). In exploratory VE objective 2, analyses for IBD (primary VE objective 2) will be stratified by medication category at index date ([Appendix 3](#)). Descriptive analyses and multivariable Cox proportional hazards regression will be conducted by strata and estimates of VE (%) will be calculated as $(1 - \text{adjusted HR}) \times 100$.

Exploratory VE objectives 3-4: For exploratory VE objectives 3-4, the incidence of PHN, disseminated HZ, HZ-related meningoencephalitis, and hospitalized HZ will be described in 2-dose (2 doses of RZV given at least 4 weeks apart) RZV vaccinated and unvaccinated adults ≥ 18 years with RA (exploratory VE objective 3) and IBD (exploratory VE objective 4). The proportion of HZ cases with PHN, disseminated VZV, VZV-related meningoencephalitis, and hospitalized HZ will also be described among RZV vaccinated and unvaccinated adults ≥ 18 years with RA and IBD. Hospitalized HZ will be evaluated in the final analysis only (i.e., not in the interim analysis).

Exploratory safety objectives 1-2: In exploratory safety objective 1, analyses for RA (primary safety objective 1) will be stratified by medication category at index date ([Appendix 3](#)) if sample size allows. In exploratory safety objective 2, analyses for IBD (primary safety objective 2) will be stratified by medication category at index date ([Appendix 3](#)) if sample size allows.

11.3. Sequence of analyses and projected study timelines

The effectiveness and safety of RZV in adults with RA or IBD (UC or CD) at KPSC will be examined, with primary VE, select secondary VE, and primary safety results for individuals ages ≥ 50 years estimated first during the first half of 2024, and full results for individuals ages ≥ 18 years to be available to GSK at the end of the study (late 2025) [Appendix 4](#).

[Appendix 4:](#) Sample size for early analyses of primary objectives among individuals ≥ 50 years of age shows sample size estimations for early analyses in individuals ages ≥ 50 years.


13. APPENDICES**13.1. Appendix 1: Abbreviations and glossary of terms****13.1.1. List of abbreviations**

5-ASA	5-aminosalicylate
ACIP	Advisory Committee on Immunization Practices
AID	Autoimmune Disease
CD	Crohn's Disease
CI	Confidence Interval
COVID-19	Coronavirus Virus Disease 2019
CSF	Cerebrospinal Fluid
DMARD	Disease-Modifying Antirheumatic Drug
EnCePP	European Network of Centers for Pharmacoepidemiology and Pharmacovigilance
EHR	Electronic Health Record
EMA	European Medicines Agency
EU PAS	European Union electronic Register of Post-Authorisation Studies
FDA	Food and Drug Administration
GPP	Good Pharmacoepidemiology Practices
GSK	GlaxoSmithKline Biologicals SA
HR	Hazard Ratio
HZ	Herpes Zoster
IBD	Inflammatory Bowel Disease
ICD	International Classification of Diseases
IRB	Institutional Review Board
JAK	Janus Kinase
KPSC	Kaiser Permanente Southern California
MTX	Methotrexate
NSAID	Nonsteroidal Anti-Inflammatory Drug
PHN	Post-Herpetic Neuralgia
RA	Rheumatoid Arthritis
RR	Relative Risk
RZV	Recombinant Zoster Vaccine

SAEs	Serious Adverse Events
SAS	Statistical Analysis System
SCCS	Self-Controlled Case Series
TNF	Tumor Necrosis Factor
U.S.	United States
UC	Ulcerative Colitis
VE	Vaccine Effectiveness
VZV	Varicella Zoster Virus
ZVL	Zoster Vaccine Live

13.1.2. Glossary of terms

Day 0	For safety objectives, the date of vaccination with the first dose of RZV
Flare	Clinically relevant new-onset flare or new-onset disease worsening of RA or IBD (UC or CD) (Appendix 2)
HZ	Herpes zoster (shingles), an often painful vesicular rash caused by reactivation of VZV persisting latently in dorsal root ganglia
Index date	For 2-dose RZV VE objectives, the index date is the date of receipt of the second dose of RZV for vaccinated individuals and their unvaccinated matches. For 1-dose RZV VE objectives, the index date is the date of receipt of the first dose of RZV for vaccinated individuals and their unvaccinated matches.
PHN	Neuropathic pain that arises from sensory (dorsal root or trigeminal ganglion cells). HZ-related pain persisting ≥ 3 months after HZ diagnosis.
RZV	A 2-dose subunit zoster vaccine containing recombinant glycoprotein E in combination with a novel adjuvant

13.2. Appendix 2: Definition of clinically relevant flare

Definition of “clinically relevant” flare

For this study, flare is defined as clinically relevant new-onset flare or new-onset disease worsening of RA (primary safety objective 1, exploratory safety objective 1) or IBD (UC or CD) (primary safety objective 2, secondary safety objective 1, exploratory safety objective 2). This definition was selected in consultation with rheumatologist and gastroenterologist experts, recognizing that new-onset disease worsening can be difficult to differentiate from flare. Trained research associates and RA or IBD specialists will review all potential flare events, according to the following case definition:

1. Contact with health care provider via documented phone call, email, telehealth visit, or in-person office, Emergency Department, or inpatient visit, AND
2. New or worsening signs and/or symptoms suggestive of a flare (at least one of the signs or symptoms below):
 - a. RA – joint swelling, joint pain/tenderness, joint stiffness.
 - b. IBD – abdominal pain/tenderness, diarrhea (increased stool frequency and/or soft or liquid stool), urgency, rectal bleeding, blood in stool, nausea/vomiting, unintentional weight loss.
 - c. Provider mention of flare, worsening of disease, recurrence, or relapse

AND

1. Change in medication for flare*:

Proposed medication regimen change/escalation algorithm for flare

- a. Intra-articular corticosteroid joint(s) injection (for RA), or
- b. Initiation of systemic corticosteroid (e.g., prednisone), or
- c. Increase in dose of baseline systemic corticosteroid (e.g., prednisone 5 mg daily to prednisone 40 mg daily with taper), or
- d. Switch in methotrexate (MTX) from oral route to subcutaneous (for RA), or
- e. Increase in dose and/or frequency of administration of any medication in current baseline regimen, or
- f. Addition of another medication to current medication regimen (e.g., MTX to current regimen of hydroxychloroquine [(Plaquenil)], biologic to current regimen of MTX), or
- g. Switch of a current medication to another medication, in the same or different category (e.g., MTX + tumor necrosis factor [TNF]-alpha inhibitor to MTX + tofacitinib; MTX + TNF-alpha inhibitor to MTX + a different TNF-alpha inhibitor)

*Exclude medication changes for any reasons other than for flare, such as acute kidney injury or other adverse effects from prior medication.

Chart review will be performed among individuals eligible for the safety analysis. Trained research associates will review medical records from health care encounters during risk windows, comparison windows, and the 30 days after a risk or comparison window (while masked to the precise window) for evidence of flare. They will identify new or worsening signs and/or symptoms suggestive of a flare and capture the date of onset of new or worsening signs and/or symptoms. They will determine whether a change in medication was made for flare by a provider. Cases with unclear sign and/or symptoms, date of onset, or change in medication for flare will be reviewed by an RA or IBD specialist.

13.3. Appendix 3: Medication categories

- a. Vaccinated and unvaccinated subjects will be matched on age, sex, race/ethnicity (if sample size allows), autoimmune disease (RA, CD, UC), and medication category (as a proxy for disease severity and risk of HZ) at the beginning of follow-up (index date). The medication categories were developed based on consultation with KPSC and external experts (rheumatologists and gastroenterologists) to ensure matching based on differences in disease severity and risk of HZ.
- b. Search period
 - Rituximab (Rituxan) or rituximab-abbs/rituximab-pvvr (Truxima): 6 months before index date¹
 - Biologics: 3 months before index date²
 - JAK inhibitors, sphingosine-1 phosphate (S1P) receptor modulators, cyclosporine: 3 months before index date to 1 month after index date³
 - Nonsteroidal anti-inflammatory drugs (NSAIDs), 5-aminosalicylate (5-ASA), aminosalicylate, sulfasalazine, thiopurines, steroids, and conventional DMARDs: Medication prescribed/refilled within 6 months prior to index date AND medication duration covers the index date⁴
- c. Medication category will be determined by the highest category of medication during the search period.
- d. Medication categories may be consolidated to ensure at least 1:1 matching.

¹Rituximab is typically dosed every 6 months, so the search period for rituximab is 6 months before the index date.

²Some biologics are given as far apart as every ~8 weeks, so the search period for biologics is 3 months before the index date.

³The search period for JAK inhibitors and S1P modulators is extended to 1 month after the index date; because JAK inhibitors and S1P modulators are associated with a significantly increased risk of HZ, [Bechman, 2019; Choden, 2022; Colombel, 2018; Curtis, 2019; Lasa, 2021; Marra, 2016; Sandborn, 2019; Winthrop, 2017; Yun, 2015] providers may administer RZV prior to initiating treatment with a JAK inhibitor or S1P modulator. Since cyclosporine is included in the same IBD medication category as JAK inhibitors and S1P modulators, the same search period will be used.

⁴While medications are typically dispensed as a ≤ 90 -day supply, some medications are occasionally dispensed as a ≥ 100 -day supply. To ensure identification of prescriptions covering the index date, medications prescribed/refilled within 6 months prior to the index date will be searched to identify those medications with a duration covering the index date.

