6.1.2. Safety

An SCCS design (Figure 1) will be used. For patients receiving only 1 dose of RZV, the date of vaccination with the first dose of RZV will be defined as Day 0, the risk period will be defined as +1 to +30 days, and comparison periods will be defined as -90 to -61 days and +31 to +60 days (Figure 1, Individuals received only one dose). The washout period will be defined as -60 to -1 days. The 30-day risk period was determined based on prior literature, vaccine mode of action, and consultation with external physician experts (rheumatologists and gastroenterologists) [Basra, 2012; Didierlaurent, 2017].

For individuals who receive a second dose of RZV within 300 days of the first RZV dose, there are several scenarios for additional risk and comparison periods. If the second dose is received between +28 to +90 days after the first dose, the risk period after the first dose will be immediately followed by a washout period up to receipt of the second dose (Figure 1, Scenario 1). If the second dose is received between +91 to +150 days after the first dose, the risk and comparison periods following the first dose will be followed by a 60-day washout period immediately before the receipt of the second dose (Figure 1, Scenario 2). If the second dose is received between +151 days to +300 days after the first dose (expected to be less common), there will be a comparison period -90 to -61 days prior to the second dose and a washout period -60 to -1 days prior to the second dose (Figure 1, Scenario 3). In Scenario 1, the risk window after the first dose could be between 28 and 30 days and the subsequent washout window could be between 0 and 60 days. In Scenario 2, the comparison window between 2 doses could be between 1 and 60 days. The maximum follow-up period will be 360 days after the first dose. Scenarios 2-4 in Figure 1 represent the maximum time period between the first and second dose

Figure 1 SCCS Design Overview for Safety Analysis

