11.1.2. Safety

The power calculation for the SCCS design is based on the signed root likelihood ratio method [Musonda, 2006]. Let k be the ratio of the length of comparison window vs. length of risk window. The number of flares that need to be observed in the risk window and comparison window to achieve 80% power is shown in Table 7 for different values of detectable RR.

Vaccination (first dose)*: Day 0

Risk period: +1 to +30 days

Comparison period: (-90 to -61 days) AND (+31 to +60 days)

Washout period: -60 to -1 days

**The current sample size calculations are based on the first RZV dose only. The design can be extended to include second RZV dose exposure. The total length of the risk windows and comparison windows will depend on the timing of receipt of the second dose.*

Table 7 Sample size required for individuals ages ≥18 years to achieve 80% power, given alpha=0.05, k=2 and different detectable RR for safety

k	RR	No. of events in the risk period	No. of events in the comparison period
2	1.2	386	643
2	1.5	87	115
2	2	34	34
2	3	16	10

No = Number; RR = Relative risk

Our SCCS design requires at least 115 events in the comparison window to achieve 80% power of detecting an increased risk of flare of RR=1.5 with a type 1 error rate of 5%.

Table 8 Estimated flares and detectable RR for safety among RA cohort ages ≥18 years who receive at least one dose of RZV

Sample size of RA cohort ¹	RA flare rate (per 30 days) ²	Number of flares in comparison window (60 days)	Detectable RR ³
3071	1.5%	92	2
3071	2.5%	154	1.5
3071	3%	184	1.5
3071	3.5%	215	1.5
3071	5%	307	1.5
3071	7%	430	1.5

RA = Rheumatoid arthritis; RR = Relative risk; RZV = Recombinant zoster vaccine

¹Sample size from [Table 5](#) (total sample size of at least 1-dose recipients).

²[[Bechman, 2018](#) ; [Bykerk, 2014](#) ; [Markusse, 2015](#); [Stevens, 2020](#)].

³Compare with [Table 7](#).

With 3071 RA patients expected to receive at least one dose of RZV during the accrual period ([Table 5](#)), there will be 154 flares in the 60 days comparison period, assuming the flare rate in RA patients is 2.5% in 30 days. This would allow us to detect an increased risk of flare of RR=1.5 (risk of flare in the risk window vs. risk of flare in the comparison window) with 80% power and 5% type 1 error rate ([Table 8](#)).

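### The flare analysis counts days -90 to -61 before dose 1 as comparison time; if some doses follow a flare by that long, the RR can be biased toward no harm, and nothing planned would show it

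*Protocol*

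**What the plan says.** For a one-dose recipient, section 6.1.2 sets the risk period at +1 to +30 days, and "comparison periods will be defined as -90 to -61 days and +31 to +60 days". It adds: "The washout period will be defined as -60 to -1 days". The 30-day risk period is given a rationale with references; the 60-day washout is not. Section 6.2.2 assigns each flare to the period of its earliest symptom onset.

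Two appendices bear on what may precede a dose. Footnote 3 of Appendix 3, explaining a medication search period, says that "providers may administer RZV prior to initiating treatment with a JAK inhibitor or S1P modulator". Appendix 2 lists, among the treatment changes that qualify an episode as a flare, "Switch of a current medication to another medication, in the same or different category"; one of its examples ends in tofacitinib, a JAK inhibitor.

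Section 11.2.2 plans "Relative risks (95% CI) for flare comparing risk and comparison periods overall and by first dose and second dose", estimated by conditional Poisson regression. Sections 5.2.1, 5.2.2 and 6.3.2 discuss time-fixed confounders, age and seasonality. They do not discuss vaccination whose timing depends on an earlier flare. Checklist item 10.8 (section 13.5.8) states that the study has no planned sensitivity analyses.

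**The concern.** A self-controlled case series assumes that an event does not alter the timing of later exposure. The protocol's own text suggests a route by which it might: a flare begins, treatment is tried, a JAK inhibitor or S1P modulator is planned, and RZV is given first. Because flares are dated to first symptoms, the interval from flare to dose includes all of those steps.

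If that interval is 60 days or less, the washout absorbs the flare. If it is 61 to 90 days, the flare counts as background. The comparison rate rises, the RR falls, and a real increase in flares after vaccination could look smaller or absent. For a primary safety objective that is the unfavourable direction. With the windows combined and no sensitivity analysis planned, an excess or a deficit in the pre-dose window would go unnoticed.

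**Working it through.** **1. Reproduce the plan's figures.** Section 11.1.2 says "The power calculation for the SCCS design is based on the signed root likelihood ratio method", and Table 7 is "given alpha=0.05, k=2 and different detectable RR for safety". Let r be the risk share of observation time, 1/(1+k) = 1/3. Then:

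- p = RR·r / (RR·r + 1 - r)
- A = 2[p·ln RR - ln(RR·r + 1 - r)]
- B = (ln RR)²·p(1-p)/A
- n = (1.96 + 0.8416·√B)² / A

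At RR 1.5: p = 0.4286, A = 0.03924, B = 1.026, n = 201.6, or 86.4 risk and 115.2 comparison events. The protocol has 87 and 115: "Our SCCS design requires at least 115 events in the comparison window to achieve 80% power". The other rows also reproduce (computed 385.9/643.2, 33.5/33.5 and 15.8/10.5; stated 386/643, 34/34 and 16/10). Tables 8 and 9 follow as N × 2 × rate: 3071 × 2 × 0.025 = 153.6 for RA and 2308 × 2 × 0.03 = 138.5 for IBD. There is no arithmetic error in the plan.

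**2. Bias for first-dose windows.** Let b be the expected flares per 30 days: RA 3071 × 0.025 = 76.8, IBD 2308 × 0.03 = 69.2. Let s be the share of recipients whose dose 1 was prompted by a flare starting 61 to 90 days earlier. **s is assumed; the documents give no value.** Extra comparison flares are X = N·s, and

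observed RR = true RR × 2b / (2b + X).

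Power = Φ[(√(nA) - 1.96)/√B], with A and B at the observed RR and n = 1.5b + 2b + X.

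| True RR 1.5 | s | X | Multiplier | Observed RR | Power |
|---|---|---|---|---|---|
| RA | 0 | 0 | 1 | 1.50 | 90% |
| RA | 0.25% | 7.7 | 0.952 | 1.43 | 82% |
| RA | 0.5% | 15.4 | 0.909 | 1.36 | 72% |
| RA | 1% | 30.7 | 0.833 | 1.25 | 46% |
| IBD | 0 | 0 | 1 | 1.50 | 87% |
| IBD | 0.25% | 5.8 | 0.960 | 1.44 | 80% |
| IBD | 0.5% | 11.5 | 0.923 | 1.38 | 71% |
| IBD | 1% | 23.1 | 0.857 | 1.29 | 51% |

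**3. What such shares require.** s is the product of the share of all recipients vaccinated because of a flare and the fraction of those flares with a 61 to 90 day lag. If that fraction were 10% (assumed), s = 0.5% needs 5% of recipients to be flare-prompted, and s = 1% needs 10%.

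**4. The opposite direction.** Write m = 1 + X/b for the flare rate in the pre-dose window relative to true background, so observed RR = true RR × 2/(1+m). If vaccination is deferred after a flare and m = 0.8, a true RR of 1.5 reads 1.5 × 2/1.8 = 1.67.

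**5. Two-dose recipients.** If the pre-dose-1 window is a fraction w of comparison time, observed RR = true RR / [1 + w(m-1)]. Figure 1 is not available here, so I assume a 30-day comparison window after dose 2. In Scenario 2 at its longest, comparison time is 30 + 60 + 30 = 120 days and w = 0.25; the three RA cases become 1.46, 1.43 and 1.36. In Scenario 1 it is 30 + 30 = 60 days, w stays at 0.5, and there is no dilution.

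**The case against.** The strongest reply is that the design already carries the main safeguard. Sixty days before dose 1 are removed from both sides of the comparison, twice the length of the risk period, so only lags of 61 to 90 days matter. No passage gives a lag of that length.

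The Appendix 3 footnote concerns matching for vaccine effectiveness, where the index date for the two-dose cohorts is dose 2. It says that providers may vaccinate first, and does not mention flare. Most early recipients were probably vaccinated routinely: RZV has been standard of care from age 50 since April 2018 (section 3.1), and 98.8% of vaccinated RA patients and 96.1% of vaccinated IBD patients in Table 2 were 50 or older. Charts for the pre-dose window are reviewed only to day -31, so a flare whose only qualifying change is a drug started after dose 1 may not be counted there. How the reference windows enter the model is also ordinary SAP content.

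Most of this stands, and it limits the point. A reader might infer that the protocol says flares trigger dose 1, or that the RR is necessarily biased downward. The documents support neither. The first is an inference from two appendices written for other purposes, and the direction of bias depends on whether flares hasten or delay vaccination.

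What remains is that the footnote describes prescribing in the same patient population. A flare first treated with steroids, with advanced therapy decided later, would qualify within the reviewed charts and is the natural long-lag case. Leaving details to the SAP does not answer item 10.8, which says in the protocol itself that no sensitivity analysis is planned.

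**Conclusion.** The point holds as a possible bias that is neither discussed nor tested, not as an established one. Half of first-dose comparison time lies in a window that flare-prompted vaccination could enrich or deferred vaccination could deplete, and the plan as written would reveal neither.

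If enrichment occurs, the error is toward no harm. For RA first-dose windows, an assumed 0.25% to 1% of recipients moves a true RR of 1.5 to 1.43 to 1.25; for IBD, to 1.44 to 1.29. At the low end, RA power is still 82%, above the 80% target. These figures assume the protocol's flare rates of 2.5% and 3% per 30 days, and the effect shrinks where a second dose adds comparison time. The change is worth making because it is cheap and bears on both primary safety objectives. It does not call for replacing the primary analysis.

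**What to change.** Keep the pooled RR as primary. In section 11.2.2 add one sensitivity analysis:

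- Fit the pre-dose comparison window (-90 to -61 before dose 1, and before dose 2 in Scenario 3) as its own level in the conditional Poisson model.
- Report flare counts in that window and its rate ratio against post-vaccination comparison time, with a 95% CI.
- Beside the primary result, report the vaccine RR against post-vaccination comparison windows only. In Scenario 1 no comparison window separates the two doses, so specify the comparison window after dose 2.
- Amend checklist item 10.8 to match, and give the reason for the 60-day washout.

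Interpret the two RRs together, without a significance rule on the pre-dose rate ratio. With 76.8 RA flares expected per 30 days, power to detect a rate ratio of 1.1 or 1.2 between two 30-day windows (r = 1/2 in the formula above) is only about 9% or 22%.

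The cost is some wording and one model term, since these windows are already chart-reviewed. The post-only RR is less precise. With one 30-day reference window (k = 1, r = 1/2, n = 2.5b, or 191.9 for RA and 173.1 for IBD), power at RR 1.5 is about 80% for RA and 75% for IBD, against 90% and 87%. It is lower still for Scenario 1 recipients, who have two risk windows to one post-vaccination comparison window. It also gives up the before-and-after balance that section 6.3.2 relies on for age and season, which is a further reason to report it alongside the primary and not in its place.
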